## 7.1.12. Clinical Laboratory Assessments

Clinical laboratory tests will be performed as specified in the Schedule of Assessments (Table 1). Additional tests may be performed as clinically indicated.

Clinical laboratory parameters (Table 3) to be obtained include:

- Hematology, chemistry, and urinalysis assessments
- Coagulation (PTT, PT, and INR) assessments
- Thyroid function tests (thyroid stimulating hormone, triiodothyronine, and free thyroxine) for clinical signs and symptoms of thyroid disorder
- Autoimmune panel

A central laboratory will be used for clinical laboratory safety assessments; local laboratories may be used for eligibility and treatment decisions. The central laboratory will provide collection supplies and perform analysis of clinical laboratory evaluations. Specimens will be appropriately processed, and laboratory reports will be provided to the Investigator. A summary of the number and volume of laboratory specimens collected at each study visit is provided in Appendix B.

The Investigator is responsible for reviewing local and central laboratory results and assessing all out-of-range findings as either clinically significant or non-clinically significant. Clinically significant laboratory results should be recorded as medical history if prior to CMP-001 dosing at W1D1 or as AEs following CMP-001 dosing at W1D1 in the eCRF.

Other Laboratory Hematology **Serum Chemistry** Urinalysis **Tests** Red blood cells (RBCs) Blood Coagulation: Alanine aminotransferase White blood cells Partial thromboplastin Glucose (WBCs) Albumin time Nitrites Differential WBC count Alkaline phosphatase Prothrombin time рΗ Total leukocyte count. International Amylase Protein including differential normalized ratio Aspartate Specific gravity Hemoglobin aminotransferase WBCs Hematocrit Thyroid Function Bilirubin Studies: Platelets Blood urea nitrogen or Microscopic battery: TSH, T3, free T4 (at serum urea RBCs, WBCs, Screening) Calcium epithelial cells, casts TSH, with reflexive Chloride (only if significant T3 and free T4 if TSH positive findings on Creatinine is abnormal (on urinalysis) Glucose treatment) Lactate dehydrogenase Lipase Autoimmune Phosphorous laboratory panel: Potassium Anti-doubled stranded DNA, antinuclear Sodium antibody, Total protein antineutrophil cytoplasmic antibody, rheumatoid factor, and antibodies to ribonucleoprotein HIV

**Table 3:** Clinical Laboratory Assessments

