Additional measures, including non-study required laboratory tests, should be performed as clinically indicated or to comply with local regulations. Laboratory toxicities (eg, suspected drug-induced liver enzyme evaluations) will be monitored during the follow-up phase via on-site/local laboratories until all study treatment-related toxicities resolve, return to Baseline, or are deemed irreversible.

If a subject shows cardiac- or pulmonary-related signs (hypoxia, abnormal heart rate, or changes from Baseline) or symptoms (eg, dyspnea, cough, chest pain, fatigue, palpitations), the subject should be immediately evaluated to rule out cardiac or pulmonary toxicity.

Some of the assessments referred to in this section may not be captured as data in the eCRF. They are intended to be used as safety monitoring by the treating physician. Additional testing or assessments may be performed as clinically necessary or where required by institutional or local regulations.

Any incidental findings of potential clinical relevance that are not directly associated with the objectives of the protocol should be evaluated and handled by the Study Investigator as per standard medical/clinical judgment.

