# 9.7.2. Clinical Laboratory Assessments

Safety central laboratory data will be summarized by treatment arm using descriptive statistics (mean, standard deviation, median, minimum, and maximum), and presented for each time point, including change from Baseline, for the Safety Analysis Set. Shift from Baseline tables will also be created. The categories in the shift tables will be WNL, Low, and High. WNL and Normal will be used when appropriate for urinalysis parameters. Clinically significant post-Baseline laboratory values will be reported as AEs. By-subject data listings of all central laboratory data will be generated and all values outside the normal range will be

flagged as High or Low. Listings of all clinically significant post-Baseline laboratory values from local and central laboratory assessments will be presented in the data listings.

Local laboratory data will be used for subject management including safety reporting and dose selection.

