CMP-001 is an investigational study drug and will be provided by the Sponsor. CMP-001 is provided as a 5 mg/mL solution in a single-use vial. Each single use vial will contain either 1.0 mL extractable volume, for a 5 mg dose of CMP-001, or 2.0 mL extractable volume, for a 10 mg dose of CMP-001. The physical

Regeneron Pharmaceuticals Inc. / Protocol: CMP-001-011 IQVIA Biotech (Confidential) Project # SZA58924

characteristics and other details about CMP-001 study drug are found in the CMP-001 Investigator's Brochure and the Pharmacy Manual.

At the end of the treatment period, study treatment will no longer be provided to subjects/Investigators unless the Sponsor chooses to extend the study. The Investigator should ensure that the subject receives appropriate standard of care to treat the condition under study.

The protocol provides additional product details in Section 6.

VI. General Analytical Considerations

Data analyses will primarily be descriptive and exploratory in nature. Categorical variables will be summarized as the number and percentage of subjects within each category of the parameter (with a category for missing data, if applicable). Continuous variables will be presented as number (n), mean, median, standard deviation, and range (minimum and maximum). Discrete variables will be presented as frequencies or proportions.

Statistical analyses will be performed using SAS® software version 9.4 or higher. MedDRA (version 23.1 or later) will be used for the coding of Medical History and Adverse Events. AEs are graded using Common Terminology Criteria for Adverse Events (CTCAE) Version 5.0. World Health Organization Drug Dictionary (WHO-DD) version B3 Global September 2020 (or later) will be used to code the Prior and Concomitant Medications, and Prior Cancer Systemic Treatments.

A. Data Sources

Data are recorded on electronic case report forms (eCRFs). Central laboratory data will be provided via electronic data transfers. Protocol Section 10.2 and Data Management Plan provide additional details regarding data recording and handling. All on-treatment disease assessments will be assessed by a BICR committee using RECIST v1.1 and provided via electronic data transfers.

B. Definition of Baseline

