Immune-mediated Adverse Events (IMAEs). IMAEs are AEs consistent with an immune-mediated mechanism or immune-mediated component for which other etiologies (e.g., infection or tumor progression) have been ruled out. IMAEs can include events with an alternate etiology which were exacerbated by the induction of autoimmunity. Information supporting the assessment will be collected on the subject's eCRF. Every AE must be assessed by the Investigator with regard to whether it is considered immune-mediated. IMAEs will be summarized based on Investigator's assessment as recorded in EDC.

The number and percentage of subjects will be tabulated by the events reported that have the greatest severity and causality. Subjects with multiple severity ratings for a given AE are counted only once under the maximum severity. At each level of subject summarization per unique SOC and preferred term, a subject is counted only once if the subject reported one or more events. Additional AESIs may be added based on the review of the safety data before the final data extract.

C. Deaths

Regeneron Pharmaceuticals Inc. / Protocol: CMP-001-011 IQVIA Biotech (Confidential) Project # SZA58924

All deaths that occur during the study or within the protocol-specified follow-up period after the last dose of the study drug will be reported. Death information to be included in the summary table concerns the incidence of deaths, along with the primary cause of death by treatment arm for the Safety Analysis Set. All deaths including deaths that occur within 100 days after the last dose of the study treatment or the initiation of an alternative new anti-cancer therapy, whichever is earlier, will be tabulated and presented in a by-subject listing, involving the primary cause of death, duration of treatment and the number of days between the last dose date of the study drug and death.

D. Clinical Laboratory Results

Safety central laboratory data will be summarized by treatment arm and overall using descriptive statistics and presented for each time point for the Safety Analysis Set. Laboratory values reported using a nonnumeric qualifier (e.g., less than [<] or greater than [>] sign), the reported numeric value will be extracted and used for analysis without the qualifier.

1. Incidence of Laboratory Abnormalities

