Gradable laboratory values will be evaluated and assigned toxicity grades according to the NCI CTCAE v5.0. Clinically significant post-baseline laboratory values will be reported as AEs. When possible, a diagnosis should be recorded as an AE, rather than the symptoms or isolated laboratory abnormalities related to the diagnosis.

Shift tables will be presented to indicate the number and percentage of patients with directional shifts in CTCAE toxicity grades relative to the baseline, when assessing the worst change (i.e., minimum and/or maximum) in the value of each laboratory test during the treatment period. With regard to laboratory parameters without CTCAE toxicity grades (e.g., serum immunoglobulin), similar shift tables will be constructed per normal range to index the shifts above or below the normal range relative to that of the baseline with the categories of < LLN, WNL and > ULN. WNL and normal will be used when appropriate for urinalysis parameters.

Summary statistics will be provided for gradable parameters with either both directions (e.g., hypocalcemia for the low value of calcium and hypercalcemia for the high value of calcium) or only one of the directions as long as the grading criteria are available per the CTCAE. Subjects will be counted only once for each criterion/direction, but the same subject can be counted for both criteria if the subject has laboratory values that meet each criterion. Subjects who meet the criteria of Grade 1 or higher for the high direction will be classified under Grade 0 for the summarization of the low direction if the CTCAE term for low direction

Regeneron Pharmaceuticals Inc. / Protocol: CMP-001-011 IQVIA Biotech (Confidential) Project # SZA58924

exists, and vice versa. Change from baseline will be calculated for each parameter of interest when both the baseline and post-baseline values are non-missing.

Additionally, a summary of Hy's Law criteria will be included to indicate if there is any subject potentially meeting Hy's Law criteria during the study for Liver Function Tests (LFTs). The components of the criteria are as follows:

- ALT or AST >= 3xULN (i.e., upper limit of normal)
- Total Bilirubin >= 2xULN
- ALP < 2xULN

Subjects potentially meeting Hy's Law Criteria is defined as those whose ALT or $AST \ge 3xULN$, Total Bilirubin $\ge 2xULN$ and ALP < 2xULN at the same visit.

2. Changes in Laboratory Values from Baseline

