Hematology and serum chemistry will be summarized in a descriptive manner for the following values that will be derived per unique subject and parameter:

[figure not shown]
- Baseline value
- Minimum post-baseline value and corresponding change from baseline
- Maximum post-baseline value and corresponding change from baseline
- Last post-baseline value and corresponding change from baseline

The baseline value will be determined using the convention described in Section VI.B. In addition, incidence of the most extreme post-baseline laboratory abnormality from the treatment-emergent period will be summarized for the corresponding parameter. A treatment-emergent laboratory abnormality is defined as a laboratory value whose grade is at least one grade higher than the baseline grade.

By-subject data listings of all central laboratory data will be generated, and all values outside the normal range will be flagged as High or Low. Listings of all clinically significant post-baseline laboratory values from local and central laboratory assessments will be presented in the data listings.

Table 3: Clinical Laboratory Assessments

Hematology	Serum Chemistry	Urinalysis	Other Laboratory
			Tests

Regeneron Pharmaceuticals Inc. / Protocol: CMP-001-011 IQVIA Biotech (Confidential) Project # SZA58924

Red blood cells (RBCs)	Alanine	Blood	Coagulation:
White blood cells	aminotransferase	Glucose	Partial thromboplastin
(WBCs)	Albumin	Nitrites	time
Differential WBC count	Alkaline phosphatase	pH	Prothrombin time
Total leukocyte count,	Amylase	Protein	International
including differential	Aspartate		normalized ratio
Hemoglobin	aminotransferase	Specific gravity	
Hematocrit	Bilirubin	WBCs	Thyroid Function
Platelets	Blood urea nitrogen or		Studies:
	serum urea	Microscopic battery:	TSH, T3, free T4 (at
	Calcium	RBCs, WBCs,	Screening)
	Chloride	epithelial cells, casts (only if significant	TSH, with reflexive
	Creatinine	positive findings on	T3 and free T4 if TSH
	Glucose	urinalysis)	is abnormal (on treatment)
	Lactate dehydrogenase		ireatificiti)
	Lipase		Autoimmune
	Phosphorous		laboratory panel:
	Potassium		Anti-doubled stranded
	Sodium		DNA, antinuclear
	Total protein		antibody,
	Total protein		antineutrophil
			cytoplasmic antibody,
			rheumatoid factor, and
			antibodies to ribonucleoprotein
			HIV
			Hepatitis B and C
A11 '	DDC 111 1 11 T	2	nepaulis B and C

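### The SAP's Hy's Law summary requires all three liver criteria at one visit, so a bilirubin rise that appears after ALT and AST have fallen, or with ALP raised, is not flagged

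*SAP*

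**What the plan says.** SAP IX.D.1 (Incidence of Laboratory Abnormalities) gives the purpose: "a summary of Hy's Law criteria will be included to indicate if there is any subject potentially meeting Hy's Law criteria during the study". The components are ALT or AST at least 3xULN, total bilirubin at least 2xULN, and ALP below 2xULN. The definition that follows counts a subject only when these coincide, ending "ALP < 2xULN at the same visit". No time window between the components is given.

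On data source, section IX.D opens: "Safety central laboratory data will be summarized by treatment arm and overall using descriptive statistics". SAP VI.A (Data Sources) adds: "Central laboratory data will be provided via electronic data transfers". The Hy's Law paragraph names no source. SAP IX.D.2 does bring in local results, but as a listing: "Listings of all clinically significant post-baseline laboratory values from local and central laboratory assessments will be presented in the data listings".

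The protocol divides the work between laboratories:

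- Section 7.1.12: "A central laboratory will be used for clinical laboratory safety assessments; local laboratories may be used for eligibility and treatment decisions".
- Section 7.4: "Laboratory toxicities (eg, suspected drug-induced liver enzyme evaluations) will be monitored during the follow-up phase via on-site/local laboratories".
- Section 9.7.2: "Local laboratory data will be used for subject management including safety reporting and dose selection".

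Protocol Table 1 schedules serum chemistry at Screening, weekly from Week 1 to Week 7, every 3 weeks from Week 10, and at end of treatment. None is marked at the 100-day, post-treatment or long-term survival follow-up contacts.

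**The concern.** The summary asks a study-wide question but answers it with a single-visit rule. If bilirubin rises after the transaminases have peaked, the two elevations can fall at different visits, and visits 3 weeks apart leave room for that. The subject then contributes nothing to the Hy's Law count.

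A zero in that table is likely to be read as showing that no candidate case occurred. Under this rule it shows only that no subject met all three criteria at one visit. The trial gives a PD-1 antibody for which the protocol supplies a hepatic management algorithm (Appendix H), and the arms are small, so no larger denominator would later expose a missed case.

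A second, lesser question is which results are screened. The section heading points to central data, while liver enzyme follow-up after treatment is local, and the paragraph does not say whether local values count.

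**Working it through.** The plan gives no figure to reproduce. The check has four parts: the logic of the rule, the effect of the visit spacing, the reach of the data, and the size.

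**1. Logic.** The SAP rule was applied to constructed visit series and compared with an illustrative windowed rule: bilirubin at least 2xULN on or within 30 days after ALT or AST at least 3xULN, with ALP below 2xULN at the ALT/AST elevation. All values are assumptions, in multiples of ULN. The ALT/AST value is the higher of the two.

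| Series | Day 0: ALT/AST, bilirubin, ALP | Day 21: ALT/AST, bilirubin, ALP | SAP rule | 30-day rule |
|---|---|---|---|---|
| Concurrent rise | 8, 2.5, 1.2 | none | flagged | flagged |
| Lag, ALT/AST still high | 8, 1.0, 1.2 | 4, 2.5, 1.2 | flagged | flagged |
| Lag, ALT/AST below 3 | 8, 1.0, 1.2 | 2.5, 2.5, 1.2 | missed | flagged |
| Lag, ALP at least 2 later | 8, 1.0, 1.2 | 4, 2.5, 2.2 | missed | flagged |
| Bilirubin rise held only at a local laboratory | 8, 1.0, 1.2 | not in the data | missed | missed |

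So a lag alone does not cause a miss. The miss needs both ALT and AST below 3xULN, or ALP at 2xULN or more, at the visit where bilirubin is high. The last row shows that a window does not help if the result is not in the data.

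**2. Visit spacing.** Assume ALT declines exponentially from a peak P (in xULN) seen at one visit. It is still at least 3xULN after g days if P × 2^(−g/h) ≥ 3, so the half-life h must be at least g / log2(P/3).

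| Peak P | g = 7 days | g = 21 days |
|---|---|---|
| 5 | 9.5 days | 28.5 days |
| 8 | 4.9 days | 14.8 days |
| 10 | 4.0 days | 12.1 days |
| 20 | 2.6 days | 7.7 days |

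For P = 8 and g = 21: log2(8/3) = 1.415, and 21/1.415 = 14.8. If ALT falls faster than this, and AST is no higher, a bilirubin rise first seen at the next visit is not flagged. The required half-life is three times longer at 3-week than at weekly spacing.

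For the window, Protocol Table 1 allows ±3 days at each 3-weekly visit, so two consecutive visits are at most 21 + 3 + 3 = 27 days apart. Its laboratory footnote allows blood to be drawn up to 72 hours before dosing, which adds at most 3 days: 27 + 3 = 30. A 30-day window therefore covers one regular interval, but not a postponed visit.

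**3. Reach of the data.** Set side by side, SAP IX.D and VI.A speak of central data. Protocol 7.1.12 allows local laboratories for treatment decisions, and Protocol 7.4 places liver enzyme follow-up with local laboratories in the follow-up phase. Table 1 has no chemistry after end of treatment. Protocol Table 2 has most cases of AST or ALT above 5xULN ending in permanent discontinuation. The later course of a marked elevation may therefore lie in local results. The documents do not settle whether those results would be screened.

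**4. Size.** SAP II.C gives 9 subjects in Arm A and 11 in Arm B, 20 treated. One case is 1/9 = 11.1%, 1/11 = 9.1%, or 1/20 = 5.0% overall.

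**The case against.** The best defence is that such a case is not lost. SAP IX.D and IX.B also plan worst-grade shift tables, maximum post-baseline chemistry values, a listing of all central results with high and low flags, the listing of clinically significant local and central values, and tables of Grade 3 or higher, serious, immune-mediated and discontinuation events. Clinically significant laboratory values are reported as adverse events. With 20 subjects, the listings can be read line by line. This stands. A reader might infer that the Hy's Law summary is the only planned display of serious liver injury; it is not. What remains is that none of the other outputs is specified to combine ALT or AST with bilirubin in the same subject.

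It can also be said that a subject with ALT at 8xULN would not wait an undisturbed 3 weeks. Protocol 5.1.4 asks for weekly re-evaluation during a nivolumab delay, and end-of-treatment assessments follow within 7 days of stopping the last study treatment. That narrows the gap without closing it. Section 5.1.4 does not say that the weekly check includes chemistry, and section 5.1.4.1 states a different minimum, with laboratory studies every 6 weeks or more often if clinically indicated. Those two passages should be reconciled. The SAP paragraph does not say whether an unscheduled draw counts as a visit.

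Finally, the window, the timing of ALP and the decline model come from neither document, and a wider rule adds false candidates. This is fair, and is why the same-visit count should stay visible.

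**Conclusion.** The point holds in a limited form. The same-visit rule can return a negative for a subject whose bilirubin rise follows the transaminase rise, provided ALT and AST are both below 3xULN, or ALP is at least 2xULN, by the time bilirubin is high. The exposure is greatest at 3-week spacing and after end of treatment. How often this would happen cannot be derived from the documents; the half-life figures rest on assumed peaks and exponential decline.

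Two stronger readings are not supported. A reader might infer that transaminase and bilirubin peaks at successive visits can never be flagged; they are flagged if ALT or AST remains at least 3xULN with ALP below 2xULN at the later visit. A reader might also infer that the screen is restricted to central data and so excludes the results most likely to show a case. The restriction is an inference from the opening of section IX.D and from VI.A, and no figure supports the consequence. The defect there is that the source is unstated.

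This is a gap in one descriptive safety table, worth correcting because a single case is 9.1% to 11.1% of an arm. It does not touch the primary endpoint.

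**What to change.** Amend SAP IX.D.1 as follows:

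- Keep the same-visit count and show it as a subset.
- Add a flag for total bilirubin at least 2xULN on or within a pre-specified window after ALT or AST at least 3xULN, with ALP below 2xULN judged at the ALT/AST elevation. Thirty days is one reasonable window; it is an assumption chosen to cover one 3-week interval with its allowances.
- Apply both rules to all scheduled and unscheduled post-baseline results held in the database, including local values where the result and its reference range are already captured.
- Footnote the table to say that uncaptured local results are not screened.

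The cost is SAP wording and one table program. Collecting every local result retrospectively is not proposed. The SAP names only a central transfer, and Protocol 7.4 says some assessments may not reach the eCRF, so that would be a larger task. The downside is a few more candidates for narrative review, including subjects with Gilbert Disease, whom inclusion criterion 4b admits with bilirubin up to 3xULN. No patient procedure changes.
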